2.1 General Design Considerations

The following is a protocol summary of the study:

Protocol title:	INTEGRRA: A Vanguard Study of Health Service Delivery in a Mobile Health Delivery Unit to Link Persons who Inject Drugs to Integrated Care and Prevention for Addiction, HIV, HCV, and Primary Care
IND Sponsor:	DAIDS
Protocol Chair(s):	[name]; [name]
Sample Size:	A total of 450 participants allotted in a 1:1 ratio to intervention and active control arms, with targets of a minimum 25% women and 25% participants under 30 years of age, and 10% people living with HIV at enrollment.
Study Population:	People living with and without HIV and who inject drugs, have OUD, and are not receiving MOUD
Study Sites:	Five urban sites in the United States (US) with substantial populations of PWID with OUD. The locations are as follows: Houston, TX; Los Angeles, CA; Bronx, NY; Philadelphia, PA; Washington, DC
Study Design:	A two-arm, individually randomized, controlled, open label study
Study Duration:	Approximately three and a half years with a possibility of extension, with individual participants on study for approximately 52 weeks (26 weeks receiving the intervention or peer navigation and then an evaluation for durability of effect at the end of 52 weeks).
Study Products:	Mobile health delivery unit ("mobile unit") to deliver "one stop" integrated health services – particularly medication for opioid use disorder (MOUD) and medication for HIV treatment and prevention – to people who inject drugs (PWID) with opioid use disorder (OUD). VS Health services available at community-based agencies
Study Regimen:	All potential study participants will provide biological samples and self-reported data via interview in the mobile unit at Screening and Enrollment Visits. Samples will be tested for HIV, hepatitis A (HAV), B (HBV) and C (HCV) and sexually transmitted infections (STIs). At the Enrollment Visit, participants who meet all inclusion and no exclusion criteria will be randomized to the intervention or active control arm and will receive harm reduction services and empiric treatment for STIs if symptomatic. Participants will also be assessed for COVID-19 at study visits; participants with suspected COVID-19 or recent

exposure will be referred for further evaluation, care and/or treatment, as available.

Intervention Arm: Participants in the intervention arm will be provided integrated health services delivered in the mobile unit and peer navigation for 26 weeks.

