2.5 Sample Size and Power

Sample sizes are chosen to provide sufficient power for both the HIV-related and MOUD-related primary outcomes. By computing sample sizes based on each individual outcome separately and choosing the largest sample size needed for either outcome, high power is achieved for both individual outcomes. Prior work in PWID populations suggests that uptake of MOUD, ART, and PrEP in the control condition will likely be modest;^{1,2} we anticipate 25% uptake of MOUD, 42.5% achieving viral suppression, and 5% uptake of PrEP in the control arm.

Sample sizes are computed to provide 90% power to detect a fifteen-percentage point difference in the proportion of participants achieving success, assuming a 5% type-I error rate (two-sided). A sample of 400 participants is needed to detect a 15-point difference in MOUD use (25% vs. 40%) between the active control and intervention arm at 26 weeks. Approximately 216 people without HIV would be needed to see a 15-point difference in PrEP uptake (5% vs. 20%). To cover both HIV and MOUD outcomes, 400 people without HIV will be needed. Approximately 10% of the study population is expected to be living with HIV – insufficient to accommodate a fully powered subgroup - but because this subgroup is expected to have very different rates of HIV-related success than the people without HIV subgroup, it will be important to analyze these participants separately. To assure 400 people without HIV, the target sample size will be augmented by 50 for a combined total of 450 participants, where 40-50 of those are expected to be people living with HIV.

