7. BASELINE DATA

Participants' baseline characteristics will be presented by site, HIV status, study arm, and overall.

- Demographics, including age, race, ethnicity, self-identified gender and sexual orientation.
- Drug use and overdose history including: the types of drugs taken (stimulants, opioids, other); ways the drugs were taken; and the number of days drugs were taken in the past month. Overdose history will be summarized by the type of drug leading to overdose on and the number of times overdosed.
- Delivery of the intervention will be described by summarizing the number of navigation sessions per participant, the location and length of the sessions, and the topics addressed.

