8. EFFICACY/EFFECTIVENESS ANALYSES

Primary Outcomes:

Among the enrolled HIV-negative cohort:

- Documented current use of MOUD defined as: alive, retained, with biological evidence of MOUD (defined in section 5) and a current MOUD prescription or proof of current receipt of MOUD from a clinic that does not provide individual MOUD prescriptions (e.g., methadone clinics) at the week 26 visit
- Current use of PrEP defined as: alive, retained, HIV-negative, with detectable PrEP (defined in section 5) at the week 26 visit

For the primary outcome of MOUD use, a Generalized Linear Model (GLM) for binary outcomes using the identity link will be performed with treatment arm and site as covariates. The proportions of participants who meet the MOUD endpoint criteria (by-arm, and by-site-by-arm) at week 26 will be provided along with the estimate and 95% confidence interval for the difference in proportions.

For the primary outcome of PrEP use, a Generalized Linear Model (GLM) for binary outcomes using the identity link will be performed with treatment arm and site as covariates. The proportions of participants who meet the PrEP endpoint criteria (by-arm, and by-site-by-arm) at week 26 will be provided along with the estimate and 95% confidence interval for the difference in proportions.

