These outcomes will be modeled and summarized using the same strategy as specified for the primary outcome in section 8 above.

- d) Decreases opioid and polysubstance use at 26 and 52 weeks

Outcome:

- Opioids (natural or synthetic) detected in urine samples for those retained at the week 26 and 52 visits (visits analyzed separately).
- Opioids (natural or synthetic) detected, along with stimulants (methamphetamine, cocaine), xylazine and/or benzodiazepines detected in urine samples at the week 26 and 52 visits (visits analyzed separately).

This objective will be analyzed only in those giving a urine sample at the respective visit (week 26 or week 52).

Opioids (natural or synthetic) include opiates, fentanyl and synthetic opioids.

Opiate detection includes 6-mam, codeine, dihydrocodeine, heroin, hydrocodone, hydromorphone, morphine, morphine glucuronide naloxone, and normorphine.

Fentanyl detection includes 4-ANPP, acetyl fentanyl, alfentanil, fentanyl, FIBF, furanyl fentanyl, methoxyacetyl fentanyl, norfentanyl, para-chlorofentanyl, para-fluorofentanyl, and valeryl fentanyl.

Synthetic Opioid detection includes isotonitazene, meperidine, metonitazene, noroxycodone, oxycodone, oxymorphone, tapentadol, tramadol, and U-47700.

Stimulant detection includes amphetamine, MDA, MDEA, MDMA, methamphetamine, methylphenidate, phentermine, benzoyllecgonine, cocaethylene, and cocaine.

Benzodiazepine detection includes alpha-hydroxyalprazolam, alprazolam, carisoprodol, chlordiazepoxide, clonazepam, diazepam, flurazepam, lorazepam, nordiazepam, oxazepam, and temazepam.

These outcomes will be modeled and summarized using the same strategy as specified for the primary outcome in section 8 above.

e) Decreases prevalence of bacterial STIs at 26 and 52 weeks

Outcome:

- Gonorrhea, chlamydia, or new or prevalent syphilis infection detected via local labs for those retained at the week 26 and 52 visits (visits analyzed separately).

This objective will be analyzed only in those giving a specimen and having a valid test result at the respective visit (week 26 or week 52).

Negative for syphilis, at any visit, is defined as a negative/not-detected non-treponemal test; or a positive non-treponemal test and a negative/not-detected treponemal test (this would be considered a false-positive test and thus considered negative for the visit).

Prevalent syphilis is defined as a positive non-treponemal test and a positive treponemal test, with a titer value $\geq 1:8$.

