Note: Participants can be non-prevalent (positive tests with tier $< 1:8$) but also not negative for syphilis. Thus, they had syphilis previously, but it is not a prevalent infection.

New syphilis is defined as a positive non-treponemal test and positive treponemal test (regardless of titer value) at a follow-up visit when they were negative at the previous visit.

These outcomes will be modeled and summarized using the same strategy as specified for the primary outcome in section 8 above.

f) Decreases fatal and non-fatal overdose events by 26 and 52 weeks

Outcomes:

- Death, with overdose as cause, collected on or before 26- and on or before 52-week visits, separately.
- Self-report of non-fatal overdose, collected on or before week 26- and on or before 52-week visits, separately.

These outcomes are reported on the SAE log form.

Death, caused by overdose, will be modeled with a time-to-event cox proportional hazards model with treatment arm as a covariate.

Person-time for fatal overdoses will be calculated as follows:

- For those retained (alive) at the visit: time between enrollment and the week 26 or week 52 visit date.
- For those reported deceased by the visit date: time between enrollment and recorded date of death.
- If deceased and no recorded date of death: time between enrollment and the midpoint of last attended visit and termination date.
- Those with no reported death and not retained at week 26 and/or week 52 (or terminated before the visit): use time between enrollment and the last attended visit (or termination date). If no other visit besides enrollment is documented: exclude from the analysis.

Note: Last attended visit can include the enrollment or week 26 visits, an interim visit, or a navigation session

Self-reported non-fatal overdoses will use a Poisson regression model (GLM with log link) with treatment arm as a covariate. We will use the number of reported non-fatal overdoses in the 30 days prior to the respective visit to compare treatment arms.

- g) Increases the proportion of participants with undetectable HCV RNA at 26 and 52 weeks among those with chronic HCV infection at enrollment

Outcome:

- Undetectable HCV RNA at the week 26 and 52 visits (visits analyzed separately) among participants with chronic HCV at enrollment.

The HCV treatment outcome will be modeled and summarized using the same strategy as specified for the primary outcome in section 8 above.

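### The between-arm models for polysubstance use (1d) and non-fatal overdose (1f) use none of the baseline drug-use and overdose data collected, and 1f also omits site, so some precision is given up

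*SAP*

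**What the plan says.** Section 8 of the SAP gives the primary model, a GLM for binary outcomes "using the identity link will be performed with treatment arm and site as covariates". For MOUD nothing more is needed, since use at enrollment is taken as zero because of the exclusion criteria.

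Section 10, 1d covers two urine-based outcomes: opioids detected, and opioids detected together with stimulants, xylazine and/or benzodiazepines. For both: "These outcomes will be modeled and summarized using the same strategy as specified for the primary outcome in section 8 above". The same sentence closes 1e (bacterial STIs).

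Section 10, 1f is different: "Self-reported non-fatal overdoses will use a Poisson regression model (GLM with log link) with treatment arm as a covariate". The outcome is the number of non-fatal overdoses reported for the 30 days before the visit. Site is not named. The HCV incidence model in 1h, also a Poisson regression, does include site, and section 2.3 stratifies randomisation by site and HIV status.

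On baseline data, section 7 lists the types of drugs taken and "the number of days drugs were taken in the past month", and adds: "Overdose history will be summarized by the type of drug leading to overdose on and the number of times overdosed". Section 2.1 says of the screening and enrollment visits: "Samples will be tested for HIV, hepatitis A (HAV), B (HBV) and C (HCV) and sexually transmitted infections (STIs)". None of these baseline values appears in a between-arm model, and no reason is given.

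**The concern.** The arm-and-site model suits MOUD, where baseline does not vary. Section 10 carries it to polysubstance use, where it may well vary. Someone who uses stimulants often at enrollment is more likely to test positive for them later, and someone with several past overdoses is more likely to report another. A covariate that predicts the outcome narrows the interval around the arm difference and corrects for chance imbalance on that covariate.

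The stake is precision on secondary outcomes for which the SAP states no power. Its sample size covers MOUD and PrEP only: "Sample sizes are computed to provide 90% power to detect a fifteen-percentage point difference". The 1f model has a further gap: it omits a factor on which randomisation was stratified, without saying why it differs from 1h.

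**Working it through.** **1. The plan's own figure.** Section 2.5 uses 25% vs 40% for MOUD, 90% power and a two-sided 5% level.

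n per arm = (z₀.₉₇₅ + z₀.₉₀)² × [p₁(1−p₁) + p₂(1−p₂)] / (p₁−p₂)² = 10.507 × (0.1875 + 0.2400) / 0.0225 = 199.6, so 200 per arm and 400 in total. This matches the SAP, but it says nothing about 1d or 1f.

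**2. Inputs for 1d.**
- Number analysed: 450 × 0.85 = 382.5, or 191.25 per arm. The 450 is from section 2.1. The 15% loss is an assumption taken from the missing-data threshold in section 3.2.
- Outcome rates: 70% vs 60%, an assumption.
- Correlation rho between baseline and outcome: 0.2 to 0.4, an assumption.

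**3. Formula.** Adjustment multiplies the variance of the arm difference by about 1 − rho², which is the same as having m = 191.25/(1 − rho²) per arm.

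Power = Φ{[0.10√m − 1.960√(2 × 0.65 × 0.35)] / √(0.21 + 0.24)}.

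At rho = 0: (1.383 − 1.322)/0.671 = 0.091, so 53.6%.

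| rho | variance × | SE × | equivalent total N | power, 70% vs 60% |
|---|---|---|---|---|
| 0 | 1.00 | 1.000 | 382 | 53.6% |
| 0.2 | 0.96 | 0.980 | 398 | 55.3% |
| 0.3 | 0.91 | 0.954 | 420 | 57.5% |
| 0.4 | 0.84 | 0.917 | 455 | 61.0% |

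Simulation (382 participants, five sites, linear risk-difference fit) gave variance ratios of 0.944 at rho 0.25, 0.852 at 0.38 and 0.818 at 0.40, close to 1 − rho². Mean estimates with and without the baseline term agreed, so under complete follow-up the omission costs precision and causes no bias.

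**4. Which baseline could help in 1d.** Everyone enrolled injects drugs, has OUD and is off MOUD, so opioid positivity at baseline may hardly vary. For two binary variables with prevalences lo < hi, the largest possible rho² is lo(1−hi)/[hi(1−lo)]. With 99% positive at baseline and 90% at follow-up it is 0.9 × 0.01/(0.99 × 0.1) = 9%. With 50% at follow-up it is 1%. These are ceilings. Non-opioid use is the better candidate.

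**5. Can the planned model carry a covariate?** Binomial identity-link fits were simulated with assumed site differences of up to 6 points either way. The share that failed or gave fitted probabilities outside 0 to 1 was:
- common outcome, 40% or 80% by baseline status: 0% without the baseline term, 0.7% with it;
- common outcome, 70% or 92% by baseline status: 0.3% without, 30% with;
- rare outcome, 6% or 25% by baseline status: 49% without, 96% with.

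The failure rate depends on how close the probabilities lie to 0 or 1, which cannot be known in advance.

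**6. Bacterial STI (1e).** Simulated rare outcomes had rho of 0.14 to 0.24. For an assumed 15% vs 8% with 190 per arm, unadjusted power is Φ(0.07/0.03253 − 1.960) = 57.6%. Multiplying the SE by √(1 − rho²) gives 58.4% to 60.1%, a gain of about 1 to 2.5 points.

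**7. Overdose (1f).** No gain is quantified, because the SAP gives no event rate. The matching baseline is also loose: section 7 states no recall period for the number of overdoses, while the outcome is a 30-day count. The model-based variance of a log rate ratio is roughly the sum of the reciprocal event counts in the two arms. It therefore barely changes when a covariate is added, and a gain would show only with a robust variance.

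**The case against.** The strongest reply is that nothing here is wrong. Arms are randomised 1:1, the comparisons are valid, the outcomes are secondary, and the size of any gain rests on correlations that the SAP does not supply. All of that stands. At rho 0.2 the gain is under two points of power. Rho of 0.5 would be optimistic: if 90% were positive at baseline and 65% at follow-up, the ceiling for a binary baseline is √[0.65 × 0.10/(0.90 × 0.35)] = 0.45.

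The baseline match is also imperfect. Section 7 names stimulants, opioids and other drugs, but not benzodiazepines or xylazine, which are part of the 1d composite. That composite also requires opioids, so baseline stimulant use predicts it only while opioid use continues. Section 7 does not list STI results either.

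A reader might infer more than the document supports:
- *That precision is lost for nothing.* Adjustment has a price under the planned link (step 5), and the SAP does not show how much the baselines vary.
- *That all these outcomes reuse the section 8 model.* 1d and 1e do; non-fatal overdose has its own Poisson model.
- *That the planned comparison is biased.* Under complete follow-up it is not. 1d is analysed only in those who give a urine sample, so dropout that differs by arm and by baseline use could distort it. The SAP has no figures that show this.
- *That the primary outcomes share the problem.* MOUD has no baseline variation. For PrEP, power at 200 per arm is already about 99.7%.

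Finally, a loosely worded adjustment in an unblinded trial would invite choosing covariates after seeing the data. This also stands, and it determines the form of the fix.

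**Conclusion.** The point holds as a modest efficiency improvement, mainly for polysubstance use. The 1d and 1f models omit baseline values that the trial collects, and 1f omits a randomisation stratum that 1h includes. For 1d the variance given up is 4% to 16% for rho of 0.2 to 0.4, which is about 2 to 7 points of power for 70% vs 60% with some 382 analysed. The rates, the correlations and the 15% loss are all assumptions. For 1f the direction is the same but the size is unknown. For 1e the likely gain is only 1 to 2.5 points, so adjustment there is optional. The planned analyses are not invalid.

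**What to change.** In section 10 of the SAP, fix one baseline covariate per outcome before outcomes are compared by arm:

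- **1d, polysubstance outcome:** use one measure of baseline non-opioid drug use as it was collected, for example past-month days of stimulant use. Do not use baseline opioid positivity. State as the main method, and not only as a fallback, a logistic model with arm, site and this covariate. Obtain the risk difference by standardising over the observed covariates, with a robust variance. The estimate stays a difference in proportions, and the planned raw proportions by arm and by site within arm can still be shown.
- **1f, non-fatal overdose:** add site and log(1 + baseline overdose count) to the Poisson model, with a robust variance, and state the recall period of the baseline count.
- **1e, bacterial STIs:** baseline STI status is optional. If it is used, apply the same standardised estimator, since the identity-link fit is fragile for a rare outcome even without it.
- **Missing baseline values:** state one simple rule, such as a missing-indicator category.

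The cost is some SAP wording, a few lines of code and a change of estimator for these secondary outcomes. No new data are needed, and the primary analyses are untouched.

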The integrated health services in the mobile unit will include:

MOUD and harm reduction services for OUD

HIV testing

HIV treatment for people living with HIV not already in care

PrEP for people without HIV

Testing and referral for vaccination or treatment for HAV and HBV

Testing and referral for treatment for HCV

STI testing and treatment

Primary care

Harm reduction services

Peer navigation in the intervention arm will coordinate and facilitate integrated care in the mobile unit through 26 weeks. As participants become established in care, navigation will help transition participants to community-based services by 26 weeks after randomization.

Active Control Arm: Participants in the active control arm will be provided 26 weeks of peer navigation to connect them to health services available at community-based agencies.

All participants (both arms) will have study visits at 26 and 52 weeks for evaluation of study endpoints.

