2.2 Study Objectives and Endpoints

Objectives:

Primary:

To evaluate whether 26 weeks of “one stop” integrated health services delivered in a mobile unit, supported by peer navigation, improves use of MOUD and increases use of PrEP, as measured at 26 weeks among people without HIV, when compared to 26 weeks of peer navigation to similar health services available at community-based agencies.

Secondary:

- 1) To evaluate whether 26 weeks of “one stop” integrated health services delivered in a mobile unit, supported by peer navigation, compared to 26 weeks of peer navigation to similar health services available at community-based agencies:
 - a) improves use of MOUD at 52 weeks
 - b) increases rates of viral suppression among people living with HIV at 26 and 52 weeks
 - c) increases use of PrEP among people without HIV at 26 and 52 weeks
 - d) decreases opioid and polysubstance use at 26 and 52 weeks
 - e) decreases prevalence of bacterial STIs at 26 and 52 weeks
 - f) decreases fatal and non-fatal overdose events by 26 and 52 weeks
 - g) increases the proportion of participants with undetectable HCV RNA at 26 and 52 weeks among those with chronic HCV infection at enrollment

- h) decreases HCV incidence at 52 weeks, for those who are HCV negative at enrollment
- 2) To evaluate whether 26 weeks of “one stop” integrated health services delivered in a mobile unit, supported by peer navigation, increases MOUD use, viral suppression, and PrEP use at 26 and 52 weeks compared to Enrollment
- 3) To evaluate whether 26 weeks of peer navigation to similar health services available at community-based agencies increases MOUD use, viral suppression, and PrEP use at 26 and 52 weeks compared to Enrollment
- 4) To document the prevalence of seropositivity for SARS-CoV-2 at baseline, 26 and 52 weeks
- 5) To document the impact of the COVID-19 epidemic on participants’ experiences of seeking, obtaining and/or maintaining health services, housing, food security and drugs
- 6) To evaluate implementation of “one-stop” integrated health services using a mobile unit, supported by peer navigation, across study sites to identify mechanisms at multiple levels to:
 - a) Guide real-time improvements and refinements in the conduct of the study to ensure primary and secondary outcomes are met with fidelity
 - b) Examine the quality and process of services delivered in each study arm, particularly as these affect primary and secondary outcomes

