1. To evaluate whether “one stop” integrated health services delivered in a mobile unit, supported by peer navigation, compared to peer navigation to similar health services available at community-based agencies, the following endpoint(s) will be assessed:
 - a. The intervention improves use of MOUD at 52 weeks
 - Documented current use of MOUD: alive, retained, with biological evidence of MOUD (any detectable medications) at the week 52 visit and a MOUD prescription current at 52 weeks after enrollment or proof of current receipt of MOUD from a clinic that does not provide individual MOUD prescriptions (e.g., methadone clinics) at the week 52 visit
 - Documented use of MOUD during the study: a MOUD prescription documented during the 52 weeks of study follow-up or proof of current receipt of MOUD from a clinic that does not provide individual MOUD prescriptions (e.g., methadone clinics) during the 52 weeks of study follow-up
 - b. The intervention increases rates of viral suppression among people living with HIV at 26 and 52 weeks
 - Among participants living with HIV at enrollment: alive, retained, and virally suppressed (VL <200 copies/mL) at the week 26 and week 52 visits, separately.
 - c. The intervention increases use of PrEP among people without HIV at 26 and 52 weeks
 - Among participants without HIV at enrollment: alive, retained, HIV negative, with detectable PrEP drugs in DBS at the week 52 visit
 - Among participants without HIV at enrollment: alive, retained, HIV negative, with protective levels of PrEP drugs in DBS samples at the week 26 and 52 visits
 - d. The intervention decreases opioid and polysubstance use at 26 and 52 weeks
 - Alive, retained, and no opioids (natural or synthetic), stimulants (methamphetamine, cocaine) or benzodiazepines detected in urine samples at week 26 and 52 visits
 - e. The intervention decreases prevalence of bacterial STIs at 26 and 52 weeks
 - Alive, retained and no evidence of gonorrhea, chlamydia, or new or recurrent syphilis infection detected at the week 26 and 52 visits

- f. The intervention reduces the rate of fatal and non-fatal overdose events by 26 and 52 weeks,
 - Death, with overdose as cause
 - Self-report of non-fatal overdose, collected at week 26 and 52 visits
 - g. The intervention increases the proportion of participants with undetectable HCV RNA among those with chronic HCV infection at enrollment

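### In SAP Section 10, item 1d, polysubstance use is a subset of opioid use, conflicts with the Section 2.2 endpoint, and leaves non-opioid drug use without an outcome of its own

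*SAP*

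**What the plan says.** The objective, in SAP Section 2.2, is that the intervention "decreases opioid and polysubstance use at 26 and 52 weeks". The SAP then turns item 1d into endpoints in two places.

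- **Section 2.2, endpoint list.** Success is "Alive, retained, and no opioids (natural or synthetic), stimulants (methamphetamine, cocaine) or benzodiazepines detected in urine samples at week 26 and 52 visits". Any one of the three named classes makes the participant a failure. Xylazine is not named.
- **Section 10, item 1d.** There are two outcomes. The first is "Opioids (natural or synthetic) detected in urine samples for those retained at the week 26 and 52 visits". The second is "Opioids (natural or synthetic) detected, along with stimulants (methamphetamine, cocaine), xylazine and/or benzodiazepines detected in urine samples at the week 26 and 52 visits". Both are modelled as in Section 8: a binary GLM with identity link, with arm and site as covariates.

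Section 10 sets the denominator: "This objective will be analyzed only in those giving a urine sample at the respective visit (week 26 or week 52"). It also says what counts as an opioid: "Opioids (natural or synthetic) include opiates, fentanyl and synthetic opioids". The analyte lists that follow name neither methadone nor buprenorphine. Only Section 10 gives an analysis for 1d.

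**The concern.** The objective has two targets, opioid use and polysubstance use, but the second outcome cannot be positive unless the first is. The mobile unit delivers "MOUD and harm reduction services for OUD" (Section 2.1), so an effect on opioid detection is what one would expect to see first. That effect can pass into the second outcome with no change in any other drug.

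Someone who stops illicit opioids while on MOUD and continues with methamphetamine and benzodiazepines moves from event to non-event on both outcomes. Such people stay in the denominator because they gave urine. Section 2.2 would count the same urine as a failure, so the two sections classify the same person in opposite ways.

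At stake is the reading of a secondary result. The trial could report less polysubstance use although non-opioid use was unchanged, or had risen among those who stopped opioids, and no Section 10 outcome would show it.

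**Working it through.** The SAP states no rate, power or sample size for 1d, so there is no figure to reproduce. The check has three parts.

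**1. Classification of a urine result for a retained participant**

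| Urine result | Section 10 opioid outcome | Section 10 polysubstance outcome | Section 2.2 endpoint |
|---|---|---|---|
| Opioid only | event | non-event | failure |
| Opioid + stimulant | event | event | failure |
| Stimulant and/or benzodiazepine, no opioid | non-event | non-event | failure |
| Xylazine only | non-event | non-event | success (not named) |
| None | non-event | non-event | success |

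The third row is the contradiction. The Section 10 columns also show that non-opioid use is invisible unless an opioid is present.

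**2. How much of an opioid effect passes through**

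P(polysubstance event) = P(opioid) × P(other drug | opioid).

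Assumed inputs, none from the SAP:
- Other-drug use q is the same in both arms and independent of opioid use, at 60% or 80%.
- Opioid detection is 85% in the control arm, against 70% or 77.5% in the intervention arm.
- There are 170 urine samples per arm. For scale, this is 85% of 200 per arm.

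SE = √[p₁(1−p₁)/170 + p₂(1−p₂)/170], with a two-sided 5% test by normal approximation.

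| Opioid detection | q | Polysubstance outcome | Apparent reduction | SE | Significant |
|---|---|---|---|---|---|
| 85% vs 70% | 60% | 0.85×0.60 = 51% vs 0.70×0.60 = 42% | 9 points | 0.0539 | about 39% |
| 85% vs 70% | 80% | 68% vs 56% | 12 points | 0.0522 | about 63% |
| 85% vs 77.5% | 60% | 51% vs 46.5% | 4.5 points | 0.0542 | about 13% |
| 85% vs 77.5% | 80% | 68% vs 62% | 6 points | 0.0516 | about 21% |

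The true difference in non-opioid drug use is zero in every row. In the first row, users of other drugs who count as non-events rise from 0.15×0.60 = 9% to 0.30×0.60 = 18%.

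Independence matters. Take q = 60% and the 15-point opioid fall. If everyone who stopped had used opioids only, the outcome would stay at 51%. If everyone who stopped was a co-user, it would drop to 51 − 15 = 36%.

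**3. Would a two-or-more-classes definition solve it?**

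At 85% vs 70% opioids and 60% other-drug use, a single other class gives 51% vs 42% again. Now spread the 60% independently over stimulants 40%, benzodiazepines 20% and xylazine 16.7%:
- P(at least one) = 1 − 0.60×0.80×0.833 = 0.60.
- P(two or more of the three) = 0.153.
- Control: 0.85×0.60 + 0.15×0.153 = 53.3%.
- Intervention: 0.70×0.60 + 0.30×0.153 = 46.6%.

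A 6.7-point difference remains with no change in non-opioid use.

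**The case against.** Everyone enrolled injects drugs and has OUD, so opioid use combined with another drug is a defensible, explicitly worded meaning of polysubstance use in this population. The opioid outcome is modelled alongside it, so a reader can see whether the two move together. This is one of several secondary outcomes, and no primary inference depends on it. All of that stands. It supports keeping the outcome under an accurate name. It does not supply a measure of non-opioid use, and seeing two nested outcomes move together does not show whether other drugs changed.

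The size is also open to challenge. The 15-point difference in the SAP's sample-size section concerns MOUD use (25% vs 40%), not opioid-negative urine. An opioid fall that large would need every additional MOUD user to become negative on the whole panel. This objection stands, and it is why the half-size case is shown.

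The direction is not fixed either. The opiate list runs "hydromorphone, morphine, morphine glucuronide naloxone, and normorphine" and so includes naloxone. Naloxone exposure could make a urine opioid-positive and push the outcome the other way. The subset structure remains whatever the list, but the sign and size of any distortion depend on it.

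A reader might infer that MOUD lowers this outcome automatically. The SAP does not support that: there is no fall if all who stop opioids were opioid-only users. A reader might also infer that the SAP as a whole scores stimulant-only or benzodiazepine-only use as success. That is true of Section 10 only, since Section 2.2 scores it as failure.

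**Conclusion.** The point holds in a limited form. Three parts rest on the text alone: the Section 10 polysubstance outcome is a subset of the opioid outcome, it disagrees with Section 2.2 for anyone using stimulants or benzodiazepines without opioids, and Section 10 has no outcome for non-opioid drugs by themselves. Section 2.2 does not fill that gap, because its composite also improves when opioid-only users stop.

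The size is illustrative: an apparent reduction of 4.5 to 12 points, reaching significance about 13% to 63% of the time. It assumes equal and independent other-drug use, 170 samples per arm and the stated opioid rates. It shrinks to nothing if no co-user stops opioids.

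It would go too far to say that the polysubstance half of 1d is wholly unanswered. Opioid co-use is measured; use of other drugs without opioids is not.

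**What to change.** 1. Reconcile item 1d between Sections 2.2 and 10. State one set of definitions, including whether xylazine counts and whether a participant without a urine sample is a failure (Section 2.2 requires being alive and retained) or is left out (Section 10).
2. Add a modelled 1d outcome at weeks 26 and 52: any stimulant, benzodiazepine or xylazine detected, regardless of the opioid result. Opioid detection does not enter this definition.
3. Label the existing combined outcome as opioid co-use, and state that it will not be read alone as evidence of reduced non-opioid drug use.

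A two-or-more-classes outcome still counts opioids and is not a substitute for step 2.

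The cost is SAP wording and one extra model per visit, on urine results already obtained. The drawback is that the added result may look less favourable to the intervention.
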